1.3 Pre-Clinical Data

In vitro studies with radiolabeled gabapentin have revealed a gabapentin binding site in areas of rat brain including neocortex and hippocampus. A high-affinity binding protein in animal brain tissue has been identified as an auxiliary subunit of voltage-activated calcium channels. However, functional correlates of gabapentin binding, if any, remain to be elucidated.

In standard preclinical *in vivo* lifetime carcinogenicity studies, an unexpectedly high incidence of pancreatic acinar adenocarcinomas was identified in male, but not female, rats. The clinical significance of this finding is unknown. Clinical experience during gabapentin's premarketing development provides no direct means to assess its potential for inducing tumors in humans.

Gabapentin was given in the diet to mice at 200, 600, and 2000 mg/kg/day and to rats at 250, 1000, and 2000 mg/kg/day for 2 years. A statistically significant increase in the incidence of pancreatic acinar cell adenomas and carcinomas was found in male rats receiving the high dose; the no-effect dose for the occurrence of carcinomas was 1000 mg/kg/day. Peak plasma concentrations of gabapentin in rats receiving the high dose of 2000 mg/kg were 10 times higher than plasma concentrations in humans receiving 3600 mg per day, and in rats receiving 1000 mg/kg/day peak plasma concentrations were 6.5 times higher than in humans receiving 3600 mg/day.

The pancreatic acinar cell carcinomas did not affect survival, did not metastasize and were not locally invasive. The relevance of this finding to carcinogenic risk in humans is unclear.

Studies designed to investigate the mechanism of gabapentin-induced pancreatic carcinogenesis in rats indicate that gabapentin stimulates DNA synthesis in rat pancreatic acinar cells *in vitro* and, thus, may be acting as a tumor promoter by enhancing mitogenic activity. It is not known whether gabapentin has the ability to increase cell proliferation in other cell types or in other species, including humans.

Gabapentin did not demonstrate mutagenic or genotoxic potential in three *in vitro* and four *in vivo* assays. It was negative in the Ames test and the *in vitro* HGPRT forward mutation assay in Chinese hamster lung cells; it did not produce significant increases in chromosomal aberrations in the *in vitro* Chinese hamster lung cell assay; it was negative in the *in vivo* chromosomal aberration assay and in the *in vivo* micronucleus test in Chinese hamster bone marrow; it was negative in the *in vivo* mouse micronucleus assay; and it did not induce unscheduled DNA synthesis in hepatocytes from rats given gabapentin.

Gabapentin has been shown to be fetotoxic in rodents, causing delayed ossification of several bones in the skull, vertebrae, forelimbs, and hindlimbs. These effects occurred when pregnant mice received oral doses of 1000 or 3000 mg/kg/day during the period of organogenesis, or approximately 1 to 4 times the maximum dose of 3600 mg/day given to epileptic patients on a mg/m² basis. The no-effect level was 500 mg/kg/day or approximately 1/2 of the human dose on a mg/m² basis.

When rats were dosed prior to and during mating, and throughout gestation, pups from all dose groups (500, 1000 and 2000 mg/kg/day) were affected. These doses are equivalent to less than approximately 1 to 5 times the maximum human dose on a mg/m² basis. There was an increased incidence of hydroureter and/or hydronephrosis in rats in a study of fertility and general reproductive performance at 2000 mg/kg/day with no effect at 1000 mg/kg/day, in a teratology study at 1500 mg/kg/day with no effect at 300 mg/kg/day, and in a perinatal and postnatal study at all doses studied (500, 1000 and 2000 mg/kg/day). The doses at which the effects occurred are approximately 1 to 5 times the maximum human dose of 3600 mg/day on a mg/m² basis; the no-effect doses were approximately 3 times and approximately equal to the maximum human dose on a mg/m² basis. Other than hydroureter and hydronephrosis, the etiologies of which are unclear, the incidence of malformations was not increased compared to controls in offspring of mice, rats, or rabbits given doses up to 50 times (mice), 30 times (rats), and 25 times (rabbits) the human daily dose on a mg/kg basis, or 4

times (mice), 5 times (rats), or 8 times (rabbits) the human daily dose on a mg/m² basis.

In a teratology study in rabbits, an increased incidence of postimplantation fetal loss occurred in dams exposed to 60, 300, and 1500 mg/kg/day, or less than approximately 1A to 8 times the maximum human dose on a mg/m² basis. There are no adequate and well-controlled studies in pregnant women. This drug should be used during pregnancy only if the potential benefit justifies the potential risk to the fetus.

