8.5 Stopping Rules.....	36
8.6 Medical Monitoring	36
9.0 Data Handling and Record Keeping	36
9.1 Confidentiality	36
9.2 Source Documents	37
9.3 Case Report Forms.....	37
9.4 Records Retention.....	37
10.0 Study Monitoring, Auditing, and Inspecting	37
10.1 Study Monitoring Plan.....	37
10.2 Auditing and Inspecting.....	38
11.0 Ethical Considerations	38
12 Study Finances	39
12.1 Funding Source	39
12.2 Conflict of Interest	39
12.3 Subject Stipends or Payments	39
13 Publication Plan	39
14 References.....	39
15 Attachments	40

List of Abbreviations

AE	Adverse Event
CFR	Code of Federal Regulations
CRF	Case Report Form
FDA	Food and Drug Administration
GCP	Good Clinical Practice
HIPAA	Health Insurance Portability and Accountability Act of 1996
ICH	International Conference on Harmonization
IDS	Investigational Drug Service
IRB	Institutional Review Board
ITT	Intent to Treat
NCCPC-R	Non-Communicating Children's Pain Checklist-Revised
PHI	Protected Health Information
REPA	Report of External Professional Activities
SAE	Serious Adverse Event
UPIRTSO	Unanticipated Problems Involving Risk to Subjects or Others

Study Summary

Title	A phase II, randomized, placebo-controlled, double blind, cross-over, study of the effects of Gabapentin on chronic irritability in neurologically impaired children
Short Title	Effects of Gabapentin on chronic irritability in neurologically impaired children.
Phase	Phase II
Methodology	The study is a randomized, placebo-controlled cross-over.
Study Duration	The estimated duration of the study is 12 months
Study Center(s)	This is a single center study to be conducted at Gillette Children's Specialty Hospital, [name].
Objectives	To determine if gabapentin provides symptom relief for chronic irritability in neurologically impaired children despite medical management for identified sources of symptoms or if no etiology is identified.
Number of Subjects	40 evaluable subjects
Diagnosis and Main Inclusion Criteria	Neurological impairment and chronic irritability suggesting pain.
Study Product, Dose, Route, Regimen	Gabapentin (Neurontin®), to be administered as an oral solution titrated over a 22 day period, followed by a 7 day stable dose period (40 mg/kg/day over 3 dosages), followed by a 9 day taper and washout period
Duration of administration	Subjects will receive drug for 34 days, and placebo for 34 days, with a 3 day washout period in between.

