1.5 Dose Rationale and Risk/Benefits

The dose protocol (see Section 5.2.) is based upon ideal dosing ranges, with sensitivity paid to titrating up and down slowly to minimize potential side effects and withdrawal symptoms. Additionally, the rationale of the increased dose in the evening is related to the known effect of inducing tiredness in some individuals. The decision to use the liquid form is to allow for tight titration of medications, and to prevent the need for "pill-splitting" to achieve precise dosing. Additionally, the liquid form may be easy to administer to patients with gastrostomy tubes. Finally, the liquid form will also be better tolerated by those patients without gastrostomy tubes but have difficulty manipulating pills.

Potential risks of Gabapentin include (from most common to least common): somnolence, dizziness, increase in hostility, nausea/vomiting, increased chance for viral infections and fevers, ataxia, fatigue, emotional lability, increased weight, and hyperkinesia.

Risks to unborn children are unknown. Therefore, parents of females who have reached puberty will be asked to allow a pregnancy test to be done. If applicable, a urine pregnancy test will be done on Day 0.

There is a risk for loss of privacy; however, study personnel will take precautions to prevent loss of privacy.

The risks of the medication are expected to be minimal compared to the benefit of relief from distressing symptoms (neuroirritability). Establishment of Gabapentin as an effective therapy for neuroirritability will help many children in the future be appropriately treated for the underlying condition without the need for other more dangerous medications (benzodiazepenes).

The patient population for this study is comprised of severely cognitively and often developmentally impaired children. Therefore, it is not applicable to screen for suicidality in this population.

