4.0 Subject Selection and Withdrawal

4.1 Inclusion Criteria

Subjects are eligible to participate in the study if all of the following conditions exist:

1. Male or female, age 1 month to 16 years at enrollment
2. Neurological impairment defined as subnormal (-2 S.D.) motor and/or cognitive ability from a variety of etiologies
3. Chronic irritability defined as symptoms suggesting pain to the child's caregiver occurring recurrently over a 4-week or greater time period
4. Subject must have an acceptable surrogate capable of giving consent on the subject's behalf

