5.2 Treatment Regimen

Doses will be given in liquid form through gastrointestinal tubes (if the child already has one) or orally. Children will be put on the following dosage regimen:

Day	Morning	Afternoon	Evening
1 - 3			5 mg/kg
4 - 6	2.5 mg/kg	2.5 mg/kg	5 mg/kg
7 - 9	2.5 mg/kg	2.5 mg/kg	10 mg/kg
10 - 12	5 mg/kg	5 mg/kg	10 mg/kg

13 - 15	5 mg/kg	5 mg/kg	15 mg/kg
16 - 18	7.5 mg/kg	7.5 mg/kg	15 mg/kg
19 - 21	7.5 mg/kg	7.5 mg/kg	20 mg/kg
22 - 28	10 mg/kg	10 mg/kg	20 mg/kg
29	7.5 mg/kg	7.5 mg/kg	20 mg/kg
30	7.5 mg/kg	7.5 mg/kg	15 mg/kg
31	5 mg/kg	5 mg/kg	15 mg/kg
32	5 mg/kg	5 mg/kg	10 mg/kg
33	2.5 mg/kg	2.5 mg/kg	10 ing/kg
34			5 ing/kg

35 - 37 off for 3 days then crossover

Weight			
Day	Morning	Afternoon	Evening
1 - 3			5 mg/kg
4 - 6	2.5 mg/kg	2.5 mg/kg	5 ing/kg
7 - 9	2.5 mg/kg	2.5 mg/kg	10
10 - 12	5 mg/kg	5 mg/kg	10 mg/kg
13 - 15	5 mg/kg	5 mg/kg	15 ing/kg
16 - 18	7.5 mg/kg	7.5 mg/kg	15 mg/kg
19 - 21	7.5 mg/kg	7.5 mg/kg	20 mg/kg
22 - 28	10 mg/kg	10 mg/kg	20 mg/kg
29	7.5 mg/kg	7.5 mg/kg	20 mg/lcg
30	7.5 mg/kg	7.5 mg/kg	15 mg/kg
31	5 mg/kg	5 mg/kg	15 mg/kg
32	5 mg/kg	5 mg/kg	10 mg/kg

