6.0 Study Procedures

Outline of procedure plan

1. Recruitment from clinics including: chronic care, neurology, gastroenterology, and pain
2. History and physical examination completed as part of routine assessment and management for chronic irritability
3. Determine if evaluation for potentially treatable causes of chronic irritability has been completed.
4. Parental consent
5. Parental questionnaire #1 and NCCPC-R rating 3 typical irritable events
6. Randomization: gabapentin or placebo
7. Titration schedule
8. Day 6 — phone call by study staff (or closest week day)
9. Day 13 — NCCPC-R, questionnaire #2, and phone call follow-up (or closest week day)
10. Day 24 — NCCPC-R, questionnaire #2, and phone call follow-up (or closest week day)
If no improvement (dose 40 mg/kg/day) begin taper early(step #11) and set up visit with Research Coordinator (Step #12)
11. Day 29 — Begin medication taper
12. Day 34 to 38 — Family comes in to meet with the Research Coordinator. Subject is weighed. Perceived benefits and side effects of the drug are discussed. Report any concerns to the PI, if any. Subject is provided new drug at this visit. The old bottle will be taken back, along with the dosing chart. Remaining drug will be measured.
13. Day 38 — Crossover
14. Repeat steps 7 —11
15. At completion Research Coordinator contacts family by telephone to discuss perceived benefits/side effects of round 2 drug. Reports concerns to PI, if any

Parents complete one questionnaire #1, four questionnaires #2, and six NCCPC-R

Questionnaire # 1: includes 60 questions that require identifying the appropriate response from the items listed and 5 questions that require a written response.

Information obtained includes: frequency and duration of pain episodes along with associated gastrointestinal symptoms and sleep disturbance. The questionnaire takes approximately 15 minutes to complete.

Questionnaire #2: includes 24 questions that require identifying the appropriate response from the items listed and 2 questions that require a written response. Information obtained includes: frequency and duration of pain episodes along with associated gastrointestinal symptoms and sleep disturbance. The questionnaire takes approximately 5 minutes to complete.

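### The only pregnancy test is timed for Day 0, so it is about 38 days old at first gabapentin exposure in the placebo-first sequence

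*SAP*

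**What the plan says.** The operative text is SAP section 1.5. It says that the risk to an unborn child is not known and, for that reason, that "parents of females who have reached puberty will be asked to allow a pregnancy test to be done". The timing follows: "If applicable, a urine pregnancy test will be done on Day 0". Section 1.3 gives the background: "Gabapentin has been shown to be fetotoxic in rodents", and "This drug should be used during pregnancy only if the potential benefit justifies the potential risk to the fetus".

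Section 4.1 admits "Male or female, age 1 month to 16 years at enrollment", so post-pubertal girls can be enrolled.

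The design has two periods. The Study Summary states: "Subjects will receive drug for 34 days, and placebo for 34 days, with a 3 day washout period in between". The dosing table in section 5.2 ends the first period with "35 - 37 off for 3 days then crossover", and section 6.0 places the crossover on Day 38. Section 5.4 describes a child who is dispensed placebo for the first period and active drug for the second. At the Day 34 to 38 visit in section 6.0 the child is weighed, the old bottle and dosing chart are handed in, benefits and side effects are discussed, and "Subject is provided new drug at this visit".

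**The concern.** A single test at enrolment suits a trial in which study drug starts the next day. Here that describes only one of the two sequences. In the other, the first 37 days are placebo and off-drug days, and gabapentin starts afterwards with no further test planned. A pregnancy that begins between Day 0 and Day 38 in a placebo-first girl would already be present at her first gabapentin dose, and the plan's only test could not have shown it.

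What is at stake is the safety of a possibly small group. The plan justifies a check by unknown fetal risk, then times it so that it stands just before exposure in one sequence and more than a month before it in the other.

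**Working it through.** The check is a day count and a search of the document for any other safeguard.

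**Inputs**
- Day of the test: 0 (section 1.5).
- Dosing table (section 5.2): titration Days 1–21 (21 days), stable dose Days 22–28 (7 days), taper Days 29–34 (6 days), off drug Days 35–37 (3 days).
- Stated crossover day: 38 (section 6.0).
- A placebo-first sequence exists (section 5.4).

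**Step 1: reproduce the crossover day.** 21 + 7 + 6 + 3 = 37 days, so the second period starts on Day 38. The Study Summary agrees: 34 + 3 = 37. The prose in section 3.1 gives 22 + 7 + 9 = 38 days, which would mean Day 39. That one-day discrepancy is a separate matter and does not change the point.

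**Step 2: age of the test at first gabapentin.** Age = day of first gabapentin − day of test.
- Gabapentin first: 1 − 0 = 1 day.
- Placebo first: 38 − 0 = 38 days.

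**Step 3: early taper.** Section 6.0 lets a child without improvement begin the taper after the Day 24 call. The document does not say when crossover then falls. Assume that the taper starts on Day 24 and keeps its 6 days (Days 24–29), followed by 3 days off (Days 30–32). The second period then starts on Day 33, and the test is 33 − 0 = 33 days old. The range is therefore roughly 33 to 38 days.

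**Step 4: does another provision close the gap?**
- Day 34 to 38 visit (section 6.0): no pregnancy test among the listed tasks.
- Schedule of Events: a medical history, NCCPC-R and Questionnaire #2 are marked for Days 34–37. There is no pregnancy-test entry on any day, including Day 0.
- Exclusion criteria (section 4.2): pregnancy is not listed.
- Exit criteria (section 4.3): acquiring an exclusion criterion leads to exit but, since pregnancy is not one, this rule does not apply.

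**Step 5: how many girls?** The document gives no number. If n post-pubertal girls are enrolled and allocation to the two sequences is equal (an assumption), about n/2 take placebo first. For an assumed n of 0 to 10 among the 40 evaluable subjects, that is 0 to 5 girls. This counts girls with an older test, not exposed pregnancies.

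**The case against.** The strongest reply is that nothing in the document conflicts. No sentence requires a test before gabapentin in each sequence. A Day 0 test and a Day 38 crossover can both be carried out as written. The test is offered with parental agreement and where applicable, and no consequence is attached to a positive result. All of this stands. A reader might infer that sections 1.5 and 5.2 contradict each other; they do not. What remains is that the stated reason for the test applies equally to both sequences, while its timing serves only one.

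Other stronger readings also fail:
- *That only placebo-first girls are at risk.* A pregnancy beginning during dosing would meet no further test in the gabapentin-first sequence either, where dosing runs from Day 1 to Day 34. The difference between sequences is confined to pregnancies already present when gabapentin starts.
- *That nothing is checked before crossover.* A medical history is marked for Days 34–37. It is not a pregnancy test, but it is a clinical review.
- *That omission from the Schedule of Events shows the test was forgotten.* The grid also has no columns for weighing, dispensing or adverse events, which the prose describes.
- *That blinding prevents staff from knowing whom this concerns.* Section 5.3 gives the research coordinator a copy of the randomization table. No procedure, however, uses it to trigger a check.
- *That section 1.3 is wrong, or shows uniform harm.* The sentence on use in pregnancy is background. The section also reports no-effect doses and, apart from hydroureter and hydronephrosis, no increase in malformations over controls.

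Nor can the gap be put down to detail left to a separate protocol. Section 1.0 calls this document a protocol, and section 1.5 fixes the timing itself.

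**Conclusion.** The point holds as a gap in coverage. The plan's own fetal-risk check is about 1 day old at first gabapentin in one sequence and about 38 days old in the other (roughly 33 to 38 under the early-taper assumption), and no other stated rule covers the interval. The day count rests on the section 5.2 table and the Day 38 crossover in section 6.0, which agree.

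Its reach is limited. It concerns only post-pubertal girls randomized to placebo first, whose number is unknown and may be small or nil. No endpoint, sample size, power or analysis is affected. It is worth correcting because it bears on participant safety and is cheap to correct.

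**What to change.** The investigators should reconcile the purpose and Day 0-only timing of the test in section 1.5 with the crossover in sections 5.2, 5.4 and 6.0 and with the Schedule of Events. The document should then state how its fetal-risk safeguard applies before first gabapentin exposure in both sequences. What that safeguard consists of, and when it is applied, is a clinical decision for the investigators.

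The cost is a small text amendment and possibly a minor added check for a few participants. An in-person visit already precedes the crossover, so no new visit is needed.

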1.4 Clinical Data to Date

Neurontin® was evaluated for the management of postherpetic neuralgia (PHN) in 2 randomized, double-blind, placebo-controlled, multicenter studies; N=563 patients in the intent-to-treat (ITT) population (Table 2). Patients were enrolled if they continued to have pain for more than 3 months after healing of the herpes zoster skin rash.

TABLE 2. Controlled PHN Studies: Duration, Dosages, and Number of Patients				
Study	Study Duration	Gabapentin (mg/day)* Target Dose Given in 3 divided doses (TM)	Patients Receiving Gabapentin	Patients Receiving Placebo
1	8 weeks	3600	113	116
2	7 weeks	1800, 2400	223	111
		Total	336	227

Each study included a 1-week baseline during which patients were screened for eligibility and a 7- or 8-week double-blind phase (3 or 4 weeks of titration and 4 weeks of fixed dose). Patients initiated treatment with titration to a maximum of 900 mg/day gabapentin over 3 days. Dosages were then to be titrated in 600 to 1200 mg/day increments at 3- to 7-day intervals to target dose over 3 to 4 weeks. In Study 1, patients were continued on lower doses if not able to achieve the target dose. During baseline and treatment, patients recorded their pain in a daily diary using an 11-point numeric pain rating scale ranging from 0 (no pain) to 10 (worst possible pain). A mean pain score during baseline of at least 4 was required for randomization (baseline mean pain score for Studies 1 and 2 combined was 6.4). Analyses were conducted using the ITT population (all randomized patients who received at least one dose of study medication). Both studies showed significant differences from placebo at all doses tested.

A significant reduction in weekly mean pain scores was seen by Week 1 in both studies, and significant differences were maintained to the end of treatment. Comparable treatment effects were observed in all active treatment arms. Pharmacokinetic/pharmacodynamic modeling provided confirmatory evidence of efficacy across all doses. Figures 1 and 2 show, these changes for Studies 1 and 2.

[figure not shown]

Figure 1. Weekly Mean Pain Scores (Observed Cases in ITT Population):
Study 1

[figure not shown]

Figure 2. Weekly Mean Pain Scores (Observed Cases in ITT Population):
Study 2

The proportion of responders (those patients reporting at least 50% improvement in endpoint pain score compared with baseline) was calculated for each study (Figure 3).

[figure not shown]

Figure 3. Proportion of Responders (patients with >50% reduction in pain score) at Endpoint: Controlled PHN Studies

No other clinical research information could be found to date for pain or irritability in non-verbal children.

1.5 Dose Rationale and Risk/Benefits

The dose protocol (see Section 5.2.) is based upon ideal dosing ranges, with sensitivity paid to titrating up and down slowly to minimize potential side effects and withdrawal symptoms. Additionally, the rationale of the increased dose in the evening is related to the known effect of inducing tiredness in some individuals. The decision to use the liquid form is to allow for tight titration of medications, and to prevent the need for "pill-splitting" to achieve precise dosing. Additionally, the liquid form may be easy to administer to patients with gastrostomy tubes. Finally, the liquid form will also be better tolerated by those patients without gastrostomy tubes but have difficulty manipulating pills.

Potential risks of Gabapentin include (from most common to least common): somnolence, dizziness, increase in hostility, nausea/vomiting, increased chance for viral infections and fevers, ataxia, fatigue, emotional lability, increased weight, and hyperkinesia.

Risks to unborn children are unknown. Therefore, parents of females who have reached puberty will be asked to allow a pregnancy test to be done. If applicable, a urine pregnancy test will be done on Day 0.

There is a risk for loss of privacy; however, study personnel will take precautions to prevent loss of privacy.

The risks of the medication are expected to be minimal compared to the benefit of relief from distressing symptoms (neuroirritability). Establishment of Gabapentin as an effective therapy for neuroirritability will help many children in the future be appropriately treated for the underlying condition without the need for other more dangerous medications (benzodiazepenes).

The patient population for this study is comprised of severely cognitively and often developmentally impaired children. Therefore, it is not applicable to screen for suicidality in this population.

